9.3 Schedule of Observations and Procedures

The schedule for all study-related procedures for all evaluations is shown in [Appendix A](#). Assessments should be completed at the designated visit/time point(s).

9.3.1 Screening

Subjects will be screened within ≤ 5 days prior to randomization. Subjects will be screened in accordance with predefined inclusion and exclusion criteria as described in Section 7.0. See Section 9.1.12 for procedures for documenting screening failures.

Procedures to be completed at Screening include:

- Informed consent.
- Demographics, medical history and medication history.
- Physical examination.
- Vital signs.
- Weight.
- Height
- ECG procedure.
- Concomitant medications.
- Concurrent medical conditions.
- Collection of blood and urine samples for hematology, serum chemistry, urine pregnancy testing (if applicable), and urinalysis.
- Assessment of Inclusion/Exclusion Criteria
- Pre-Treatment Events

9.3.2 Randomization

Randomization will take place on Day1 (could be the same day at which Screening visit took place). The following procedures will be performed and documented during Randomization:

- Vital Signs (if not same day as Screening procedures).
- Concomitant medications.
- Adverse Events.
- The following parameters will be assessed by the investigator: presence of muscle spasm, presence of local pain, limitation of activities of daily living, and limitation of range of motion.
- Subject Diary dispense. Subjects should be instructed :
 - To complete assessment for Day 1 at the hospital before the first drug intake.
 - Starting from Day 2 record the following assessments (compared to Baseline) in the daily diary: rating of medication helpfulness, relief from local pain, subject-rated Clinical global impression, restriction in activities of daily living, and restriction of movement;
 - To record the following assessments in the daily diary: **Company Confidential Information** intensity of local pain **Company Confidential Information** ;
 - To complete their diary during 14 days at the same time each day if possible but record the worst feeling/symptom since the diary was last completed. No diary to be completed at Day 15 (Visit 4) but returned to the Investigator.
 - To bring their diary to each study visit for review by Investigator. Completed pages will be collected by Investigator, then the diary will be dispensed to subject again.
- If the subject has satisfied all of the inclusion criteria and none of the exclusion criteria for randomization, the subject should be randomized using the IVRS/IWRS, as described in Section 8.2.
- Study drug dispense. The medication identification (ID) number of the study drug will be provided via IVRS/IWRS. To avoid any overdose and non-compliance with study drug intake, original bottle containing 60 capsules with CER 15 mg or Placebo will be opened in front of the subject and 40 capsules of 60 will be removed in cleanliness condition and put into the additional bottle for keeping at the site (never dispensed to subject) until destruction. Original bottle containing 20 capsules with CER 15 mg or Placebo will be dispensed to subject. Subject will be instructed to:
 - To swallow one capsule whole with 180 mL of room temperature water, once daily in the evening between 18:00 and 19:00 starting from Day1.
 - To take the study drug for 14 days, even if complete relief has been achieved earlier. The last day of study drug intake should be Day14 in the evening.
 - Not to open/crush the capsules at any time.
 - To bring all unused study medication to each study visit.
 - Subjects will be warned that the study medication might impair mental and/or physical abilities required for performance of hazardous tasks, such as operating machinery or driving a motor vehicle.

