5.2 Endpoints

5.2.1 Primary Endpoints

- The percentage of subjects with subject's rating of medication helpfulness impression on Day 3 of treatment.

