6.2 Justification for Study Design, Dose, and Endpoints

- Study design including primary and secondary criteria for evaluation and methods of measurement will be similar to previous pivotal Cyclobenzaprine studies in order to determine positive efficacy trend of Cyclobenzaprine 15 mg versus Placebo;
- The randomized, double-blind, parallel, placebo-controlled design will reduce bias in different treatment regimens with respect to efficacy and safety. Randomization will provide maximum assurance that subject characteristics are similar across the treatment groups. Blinding subjects and all study personnel who will be involved in their assessment to the study treatment will maintain the objectivity of the assessment;
- A placebo arm has been added, since the primary endpoint is a subjective score and the placebo control allows to better evaluate the treatment effect of Cyclobenzaprine;
- A placebo arm is acceptable because the study is of short duration and the cervical and/or lower back pain due to muscle spasms is not considered a life-threatening condition if untreated. Moreover, rescue therapy will be implemented in lack of efficacy cases before subject is discontinued from the study;
- The dose level of Cyclobenzaprine 15 mg once daily is chosen for this study as the approved dose for the treatment of the pain due to muscle spasms of local origin. The Cyclobenzaprine 15 mg once daily has shown its efficacious and safe in adult patients with the pain due to muscle spasms, so it is expected that the same dose will be effective and safe in Russian patients.

The endpoint assessment for this study will take place on Day 3 instead of Day 4 (as utilized in 1105 and 1106 studies) which is based on cyclobenzaprine MR 30 mg pharmacokinetic parameters T_{max}

= 10.5 ± 3.32 hours and $t_{1/2} = 27.7 \pm 8.56$ hours and implies capturing probable earlier clinical effects of the drug than it was shown in previous studies.

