9.1.6 Primary Efficacy Measurement

The measures of effectiveness in this study will include:

- **Subject's rating of medication helpfulness:**

Subjects will be asked to assess it on a daily basis (in the daily diary), using the following 5-point rating scale: "How would you rate this study medication in improving your condition?"

"0 = poor"

"1 = fair"

"2 = good"

"3 = very good"

"4 = excellent"

Assessment of the subject's answers will be made for the Day 3, 7 and 15.

- **Physician's clinical global assessment :**

The investigator will be asked to assess their clinical global impression of change compared to Baseline, based on physical examination, degree of muscle spasm (presence of muscle spasm assessment), reaction to palpation (presence of local pain assessment), limitation of range of motion, and evaluation of the patient's reported functional assessment (limitation of activities of daily living assessment). The following 5-point rating scale will be used:

"1 = worse"

"2 = no change"

"3 = slight improvement"

"4 = moderate improvement"

"5 = marked improvement"

Assessment will be made for the Day 3, 7 and 15.

- **The subject-rated relief from local pain:**

Subjects will be asked to assess on a daily basis (in the daily diary) their level of relief from local pain due to the muscle spasm (in either the lower back or cervical spine) compared to Baseline (Visit 1) using the following 5-point rating scale:

"1 = no relief"

"2 = a little relief"

"3 = some relief"

"4 = a lot of relief"

"5 = complete relief"

Assessment of the subject's answers will be made for the Day 3, 7 and 15.

- **The subject-rated restriction in activities of daily living:**

Subjects will be asked to assess on a daily basis (in the daily diary) the change in the severity of restriction in the activities of daily living compared to Baseline (Visit 1) using the following 5-point rating scale:

"1 = worsening"

"2 = no change"

"3 = mild improvement:"

"4 = moderate improvement"

"5 = marked improvement"

Assessment of the subject's answers will be made for the Day 3, 7 and 15.

CONFIDENTIAL

- **The subject-rated restriction of movement:**

Subjects will be asked to assess on a daily basis (in the daily diary), the change in restriction of movement due to the muscle spasm compared to Baseline (Visit 1) using the following 5-point rating scale:

“1 = no relief”

“2 = a little relief”

“3 = some relief”

“4 = a lot of relief”

[figure not shown]
“5 = complete relief”

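### The recall period of the Day 3 primary diary rating is unclear, and its position relative to the evening dose is not fixed

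*Protocol*

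**What the plan says.** Section 5.2.1 names a single primary endpoint: "The percentage of subjects with subject's rating of medication helpfulness impression on Day 3 of treatment". Section 9.1.6 defines it as a 0-4 diary rating in answer to "How would you rate this study medication in improving your condition", with no recall window in the question.

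Section 9.3.2 holds the diary instructions:

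- The first entry: "To complete assessment for Day 1 at the hospital before the first drug intake".
- The change and helpfulness items: "Starting from Day 2 record the following assessments (compared to Baseline) in the daily diary: rating of medication helpfulness". The same bullet lists relief from local pain, global impression, restriction in daily activities and restriction of movement.
- Pain intensity is in a separate bullet, without the reference to Baseline.
- A later bullet, not limited to any item, says the diary is to be completed "at the same time each day if possible but record the worst feeling/symptom since the diary was last completed".

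The same section has the capsule taken "once daily in the evening between 18:00 and 19:00 starting from Day1". At Visit 2 (Section 9.3.3) the investigator reviews the diary, takes the pages already completed and hands the diary back. Section 6.2 explains the move of the endpoint from Day 4 to Day 3 by pharmacokinetics and says that this "implies capturing probable earlier clinical effects of the drug than it was shown in previous studies".

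**The concern.** A worst-since-last-entry rule is natural for a 0-10 pain intensity score. It fits poorly with a rating of how well the medication has worked, or of relief or improvement against Baseline. A subject given both instructions has to choose between the worst point of the past day and the present state. In a condition that tends to improve, the worst point will often lie early in the window. Different readings would then be scored together as Day 3.

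The timing is also loose. A daily entry whose hour is free, next to a capsule taken at a fixed hour, lets ratings with the same day number follow different numbers of doses. This matters most early in treatment, and Section 6.2 chose Day 3 to look for an early effect. The time-to-improvement analyses in Section 13.1.3 for helpfulness and for relief from pain count days on ratings from the same diary, so they share the ambiguity.

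**Working it through.** The protocol states no number of doses before the Day 3 rating, so there is no planned figure to reproduce. The check is a count of doses and hours.

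**Inputs.** Doses on Days 1, 2 and 3 at clock hour d, between 18 and 19 (Section 9.3.2). Day 3 entry at clock hour h. Assumption: the Day 2 entry was made 24 hours earlier, as a constant daily time implies.

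**Formulas.**
- Doses taken: 2 if the entry precedes the Day 3 capsule, 3 if it follows it.
- Hours since the first dose: 48 + h - d.
- Hours of Day 2 inside the look-back: 24 - h.
- Hours of the look-back before the second dose: d - h, or 0 if negative.

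| Day 3 entry | Doses taken | Hours since first dose | Look-back hours in Day 2 | Look-back hours before second dose |
|---|---|---|---|---|
| 08:00 | 2 | 37-38 | 16 | 10-11 |
| 12:00 | 2 | 41-42 | 12 | 6-7 |
| 17:30 | 2 | 46.5-47.5 | 6.5 | 0.5-1.5 |
| 21:00 | 3 | 50-51 | 3 | 0 |

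An entry between 18:00 and 19:00 follows two or three doses, depending on whether the capsule has been taken.

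**Recall.** If the subject applies the worst-since-last-entry rule to helpfulness, the window reaches into Day 2 at every clock time. For any entry before the evening capsule, part of the window precedes the second dose. If the subject ignores the rule for this item, the rating describes the present. The text does not settle which applies: the rule is worded for feelings and symptoms, but it exempts no item.

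**Number of doses.** The Day 1 entry is made before the first capsule. A subject who keeps that hour stays before the evening dose and has taken two doses at the Day 3 rating. Three features leave the other case open: the constant hour is asked for only where possible, later entries need not be made at the site, and Section 9.3.3 does not require the Day 3 page to be finished by Visit 2.

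**Size.** A power effect would need the share of subjects on each reading, the share writing after the capsule, and the change in the treatment difference that results. The document gives none of these.

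**The case against.** The strongest reply is that the text, read sensibly, already works. Helpfulness is neither a feeling nor a symptom. Its question has no look-back, and Section 9.3.2 lists it among the items rated against Baseline, apart from pain intensity, where a worst-moment rule fits. The pre-dose Day 1 entry and the constant hour point to two doses for everyone who follows them. The diary form is not in the document, so its item wording may be clearer. Section 6.2 describes the measurement methods as similar to the earlier pivotal studies. If study 1106 used the same rule, any attenuation from it is already in the difference assumed in Section 13.3.

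Most of this stands, and it limits the point to unclear wording and a permitted range of timing. It does not remove the point: the rule is written for the diary as a whole, and the constant hour is optional.

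A reader might infer more than the document supports:

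- **That the Day 3 rating does rest on two doses in some subjects and three in others.** The text allows this; it does not show that it happens.
- **That the rating is fixed on Day 2 and pushed toward the low end.** That is one reading of an unclear rule.
- **That power falls by a known amount.** With power = Φ((1 - f) × (1.960 + 0.842) - 1.960), a loss f of 10% or 20% of the assumed difference would take 80% to about 71% or 61%. These values of f are pure illustration; no figure in the document supports them. Modelled drug levels do not help either, because the protocol gives no relation between exposure and effect.
- **That the Day 3 physician assessment cannot support the primary result.** The confirmatory analysis in Section 13.1.3 is the responder analysis of the same subject rating. Nothing requires the physician's separate secondary assessment to describe the same moment.

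**Conclusion.** The point holds as a defect of wording in how the primary endpoint is collected. As written, the protocol leaves the recall period of the Day 3 helpfulness rating open, and it permits two or three prior doses under one day label, with two the more natural reading. Randomized, blinded arms receive the same instruction, so the expected consequence is added noise or possible dilution of the difference, not bias in favour of either arm. The size cannot be derived from the document.

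The dose count rests only on the stated dosing hours; the look-back figures also assume entries 24 hours apart. The matter is worth correcting before enrolment because an analysis plan cannot recover, after data collection, which recall period each subject used.

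**What to change.** In Section 9.3.2 and on the diary pages:

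1. Limit the worst-since-last-entry rule to symptom-intensity items, such as pain intensity.
2. State that helpfulness, relief from local pain, global impression, daily activities and movement are rated as the present state compared with Baseline.
3. Have each daily entry, including Day 3, completed before that day's capsule, in line with the pre-dose Day 1 entry.
4. Record the completion time.

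Dosing is unchanged, and no visit or procedure is added. For subjects who took every dose, the Day 3 rating then follows exactly two doses, and in general the Day n rating follows n - 1. With "The last day of study drug intake should be Day14 in the evening", the Day 14 rating would follow 13 of the 14 capsules. The hour before the capsule stays free, so time since the first dose still varies (37-38 hours for an 08:00 entry, just under 48 hours for an entry immediately before the Day 3 capsule with a constant dosing hour). The recorded time allows this to be described.

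The cost is a paragraph of protocol text and reprinted diary instructions. The downside is that the ratings may be less comparable, word for word, with the earlier studies if those used the same recall rule.

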9.3.3 Visit 2 (Day 3) and Visit 3 (Day 7)

Subjects will visit the clinic on Day 3 and on Day 7. The following assessments will be performed at the both visits:

- Vital Signs.
- concomitant medications.
- Adverse Events.
- The investigator will assess: presence of muscle spasm, presence of local pain, limitation of activities of daily living, and limitation of range of motion.
- Physician's clinical global assessment based on presence of muscle spasm, presence of local pain, limitation of range of motion, and limitation of activities of daily living will be recorded.
- Subject diaries will be reviewed. Completed pages will be collected by Investigator, then the diary will be dispensed to subject again.
- Study drug returned and medication compliance checked, then study drug will be dispensed again.

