9.3.4 Visit 4 (Day 15) or Early Termination

The Visit 4 will be performed on Day 15 or at the Early Termination Visit. The following procedures will be performed and documented:

- Physical examination.
- Vital signs.
- Weight
- Collection of blood and urine samples for hematology, serum chemistry, urine pregnancy testing (if applicable), and urinalysis.
- Inquiry regarding any concomitant medications.
- Inquiry for Adverse Events.
- ECG procedure.
- The investigator will assess: presence of muscle spasm, presence of local pain, limitation of activities of daily living, and limitation of range of motion.
- Physician's clinical global assessment based on presence of muscle spasm, presence of local pain, limitation of range of motion, and limitation of activities of daily living was recorded.
- Subject diary collection and review.
- Unused study drug return and compliance calculation.
- For all subjects receiving study medication, the investigator must complete the End of Study (e)CRF page.

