10.2.1.2 PTE and AE Reporting

At each study visit, the investigator will assess whether any subjective AEs have occurred. A neutral question, such as “How have you been feeling since your last visit?” may be asked. Subjects may report AEs occurring at any other time during the study. Subjects experiencing a serious PTE must be monitored until the symptoms subside and any clinically relevant changes in laboratory values have returned to baseline or there is a satisfactory explanation for the change. Non-serious PTEs, related or unrelated to the study procedure, need not to be followed-up for the purposes of the protocol.

All subjects experiencing AEs, whether considered associated with the use of the study medication or not, must be monitored until the symptoms subside and any clinically relevant changes in laboratory values have returned to baseline or until there is a satisfactory explanation for the changes observed. All PTEs and AEs will be documented in the PTE/AE page of the (e)CRF, whether or not the investigator concludes that the event is related to the drug treatment. The following information will be documented for each event:

1. Event term.
2. Start and stop date.
3. Severity.
4. Investigator’s opinion of the causal relationship between the event and administration of study medication(s) (related or not related) (not completed for PTEs).
5. Investigator’s opinion of the causal relationship to study procedure(s), including the details of the suspected procedure.
6. Action concerning study medication (not applicable for PTEs).
7. Outcome of event.
8. Seriousness.

Patient diaries will not be used as a primary means to collect AEs. However, should the investigator become aware of a potential AE through the information collected with this instrument, proper follow-up with the patient for medical evaluation should be undertaken. Through this follow-up if it is determined that an AE not previously reported has been identified, normal reporting requirements should be applied.

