As long as no controlled studies of cyclobenzaprine use in pregnant women have been performed, it should not be taken during pregnancy.

Lactation

Stop breastfeeding during treatment with cyclobenzaprine, as far as no data of drug permeability to breast milk are available.

Posology and administration

Per os, without chewing, washing down with a small amount of water.

1 capsule of Myorix® in a dose of 15 mg once a day. Some patients might need dose increase up to 30 mg/day. In this case, take 1 capsule of Myorix® in a dose of 30 mg once a day, or 2 capsules of Myorix® in a dose of 15 mg once a day.

It is recommended to take the drug at the same time of a day. Treatment course duration - not more than 2 - 3 weeks.

Adverse reaction

Incidence of side effects of the drug is evaluated as follows:

Very often: $\geq 1/10$,

Often: $>1/100$, $<1/10$;

Not often: $>1/1000$, $<1/100$;

Seldom: $\geq 1/10\ 000$, $< 1/1000$,
Very seldom: $< 1/10\ 000$.

General disorders:

Not often: faintness, sickliness, chest pain, edemas;

Cardiovascular system disorders:

Not often: tachycardia, fibrillation, vasodilation, rapid heartbeat, arterial hypotension/hypertension, myocardial infarction, myocardial conduction defect, stroke;

Disorders of gastrointestinal tract:

Very often: dry mouth;

Often: constipation, nausea, dyspepsia, bad taste;

Not often: vomiting, anorexia, diarrhea, abdominal pain, gastritis, thirst perception, bloat, paraglossa, liver dysfunction;

Seldom: hepatitis, jaundice, cholestasis, paralytic ileus, discoloration of tongue, stomatitis, parotiditis;

Endocrine system disorders:

Not often: syndrome of inappropriate antidiuretic hormone;

Disorders of blood and lymphatic system:

Not often: purpura (hemorrhagic rash), myelosuppression, leukopenia, eosinophilia, thrombocytopenia;

Immune system disorders:

Not often: hypersensitivity response in the form of anaphylactic edema or angioedema, itching, facial edema, urticaria, rash;

Metabolism and nutritional disorders:

Not often: high or low blood glucose level, increased or reduced body weight;

Musculoskeletal system disorders:

Not often: local muscle weakness, myalgia;

Nervous system and mental disorders:

Often: drowsiness, dizziness, increased fatigability, asthenia, blurred vision, headache, nervousness, confused consciousness;

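### At Visits 2, 3 and 4/Early Termination the investigator both asks about adverse events and gives the subjective physician ratings, with no rule that the ratings come first

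*Protocol*

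**What the plan says.** - **Visits 2 and 3 (Protocol 9.3.3).** Under "The following assessments will be performed at the both visits" come vital signs, concomitant medications and adverse events. Next is "The investigator will assess: presence of muscle spasm, presence of local pain, limitation of activities of daily living, and limitation of range of motion", then the physician's clinical global assessment, then diary review and drug return.
- **Visit 4/Early Termination (9.3.4).** The concomitant-medication item and "Inquiry for Adverse Events" stand above the ECG, the four investigator ratings and the global assessment. Diary collection comes after them.
- **Who asks about adverse events (10.2.1.2).** "At each study visit, the investigator will assess whether any subjective AEs have occurred".
- **Who rates (9.1.6).** The investigator gives the global impression of change on a 5-point scale. It rests on examination, spasm, reaction to palpation, range of motion and reported function.
- **Continuity (9.1).** For each procedure the same investigator or site staff member should assess a subject where possible. No separate efficacy assessor is named.
- **Blinding (6.2).** Blinding of everyone involved in the assessment "will maintain the objectivity of the assessment". The stated means are the IVRS/IWRS (8.4) and identical capsules (8.1.1.3).
- **Known side effects (Appendix E).** "Very often: dry mouth", a class defined as at least 1 in 10. Drowsiness and dizziness are in the next class, between 1 in 100 and 1 in 10.
- **Endpoints.** The Day 3 physician's global assessment is listed first among the secondary endpoints (5.2.2). It is analysed in the same way as the primary endpoint (13.1.3).

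**The concern.** Identical capsules and a central allocation system hide the treatment code. They do not stop an investigator from guessing the arm when a subject reports a dry mouth or drowsiness. If that report comes just before the investigator grades spasm, tenderness and overall change, the grade can drift with the guess. All of these scales call for judgement.

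Any such drift would favour the active arm if side effects are commoner there and the rater takes them as a sign of active drug. It would enter a formal Wilcoxon comparison of the physician's global assessment, which is the physician's counterpart to the subject-rated primary endpoint. Section 6.2 counts on blinded assessors for objectivity, but no procedural rule protects the ratings from side-effect information.

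**Working it through.** **1. Which visits matter.**

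| List | Efficacy ratings by investigator? | Adverse-event item above them? | After dosing? |
|---|---|---|---|
| Screening (9.3.1) | No; only "Pre-Treatment Events" | Not applicable | No |
| Randomization (9.3.2) | Yes, baseline | Yes | No; dosing is "once daily in the evening between 18:00 and 19:00 starting from Day1" |
| Visits 2 and 3 (9.3.3) | Yes | Yes | Yes |
| Visit 4/Early Termination (9.3.4) | Yes | Yes | Yes |

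Only the last two rows can carry the risk. Day 3 is the first scheduled visit after dosing starts, so no post-dose adverse-event inquiry is scheduled before it. On Days 7 and 15 the investigator may already remember earlier reports.

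**2. How much one side effect reveals.** Allocation is 1:1 (6.1). Let p_C and p_P be the probabilities of reported dry mouth on CER and placebo.

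- P(CER | dry mouth) = p_C / (p_C + p_P)
- P(correct guess from dry mouth alone) = 0.5·p_C + 0.5·(1 − p_P)

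The protocol gives only a class of at least 10% for the drug and no placebo rate. I assume p_C from 10% to 30% and p_P from 1% to 10%.

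- Least informative (10%, 10%): 0.10/0.20 = 0.50; correct guess 0.05 + 0.45 = 50%.
- Most informative (30%, 1%): 0.30/0.31 = 0.97; correct guess 0.15 + 0.495 = 64.5%.

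A report can therefore be telling for the subject who makes it. Over all subjects, guessing stays between chance and about 65%.

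**3. What that could do to the test.** This is a simulation under assumptions, because the protocol gives no figure to reproduce. There is no true effect and 90 subjects per arm. The ratings on the 1–5 scale are distributed 5/25/30/25/15%. A stated share of subjects with an adverse event is scored one category higher, capped at 5. The test is a tie-corrected Wilcoxon test at two-sided 0.05. With 15% already at the top category, the mean shift between arms is (difference in event rates) × (share upgraded) × 0.85.

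| Adverse events, CER vs placebo | Share upgraded | Mean shift (categories) | False-positive rate |
|---|---|---|---|
| No upgrading | 0 | 0 | about 5% |
| 20% vs 5% | half | 0.15 × 0.5 × 0.85 = 0.06 | about 7% |
| 30% vs 10% | quarter | 0.20 × 0.25 × 0.85 = 0.04 | about 6% |
| 40% vs 10% | quarter | 0.30 × 0.25 × 0.85 = 0.06 | about 7% |
| 30% vs 10% | half | 0.20 × 0.5 × 0.85 = 0.09 | about 8% |
| 40% vs 10% | half | 0.30 × 0.5 × 0.85 = 0.13 | about 11–12% |
| 40% vs 10% | all | 0.30 × 1 × 0.85 = 0.26 | about 32% |

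The result follows the product of event contrast and rater behaviour. The documents supply neither.

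**4. What is not affected.** The primary endpoint is a diary rating by the subject, who knows his or her own side effects whatever the order of the visit. The four component ratings are only summarised by counts and percentages (13.1.3), so no test of them can be inflated.

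**The case against.** **The lists are not a timetable.** This stands. The bullets are unnumbered. Where 9.3.3 means a sequence it says so inside a bullet, as with re-dispensing after review. The Randomization list shows that layout is not chronology: it carries an adverse-event item on Day 1, although 10.2.1.1 starts adverse-event collection at first administration. A reader might infer that the protocol makes the investigator hear of side effects before scoring; the text does not say that. The converse also holds: nothing prevents it, and a site working down the page would do it.

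**One role is not one person.** This stands in part. Section 9.1 allows the investigator or site personnel for each procedure. One individual doing both tasks is likely but not prescribed.

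**Ratings-first would not seal the rating.** This stands. Limitation of daily living is rated partly by questioning the subject (9.1.6), and drowsiness or dizziness can surface there. On Days 7 and 15, earlier reports are remembered.

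**The endpoint is modest and the numbers are assumed.** This stands. Section 13.1.3 treats the physician's global assessment under other efficacy endpoints. If the Day 3 visit precedes that evening's dose, about two capsules have been taken, and nothing in the protocol supports event rates of 30–40% by then.

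These points limit the weight of the concern. They do not supply the missing safeguard.

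**Conclusion.** The point holds as a small improvement at no cost. At Visits 2, 3 and 4/Early Termination, adverse-event inquiry and subjective rating fall to one role. The inquiry is listed above the rating, and neither a ratings-first rule nor a separate assessor is provided, although 6.2 leans on assessor blinding and Appendix E names recognisable side effects.

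The benefit of a change is mainly for the Day 3 physician's clinical global assessment. It is partial on Days 7 and 15, and incomplete throughout because the daily-living rating needs questioning.

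The size cannot be fixed from the protocol. On the assumptions shown, the false-positive rate of that test is about 5% to 12% when a quarter to half of subjects with events are scored one category higher. It is about 32% only if event rates are 40% vs 10% and every such subject is upgraded. These rates charge all the bias to side-effect knowledge and should be read as illustration.

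A reader might go further and infer that the blind is broken, or that the primary result is at risk. The documents support neither: capsules are identical, allocation is central, any inference from side effects is partial, and the primary endpoint is rated by the subject.

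**What to change.** In 9.3.3 and 9.3.4, add one sentence: the four investigator ratings and the physician's clinical global assessment are completed and recorded before the adverse-event inquiry, the concomitant-medication inquiry and the diary review. Move the adverse-event and concomitant-medication bullets below the ratings in both lists. Diary review already stands below them, so the sentence only makes that order explicit.

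The cost is an edit to two lists and a line in site training. No extra staff, visit or data item is needed, and adverse-event collection is otherwise unchanged. Anything a subject volunteers while being rated is still recorded as usual. The training line should acknowledge that questioning about daily activities remains part of the rating, so the separation will not be complete.
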